Our target population consists of patients with a known diagnosis of cancer who were seen at the study site after Aug 1, 2021. Our study will employ the following inclusion criteria:

- Above the age of 18
- Meet one of the sub-criteria below:
 - Meet the CDC definition for immunocompromised status for cancer patients, i.e patients receiving active treatment for solid tumor or hematologic malignancy OR
 - Be a recipient of stem cell transplant or CAR-T cell therapy in the last 2 years OR
 - Have a negative SARS-CoV-2 spike IgG despite standard vaccination series, irrespective of active/inactive cancer status, on observation, or active therapy.
- Underwent an in-person encounter at a study facility during the study period
- Have received the second of the mRNA vaccines (BNT162b2 or mRNA 1273) or the adenoviral Ad26CoV2.S vaccine at least 28 days before the booster dose.

Exclusion Criteria

- Patients who have had a serious adverse reaction to any prior COVID-19 vaccines resulting in emergency room visit or hospitalization, had events related to myocarditis, thrombosis and thrombocytopenia syndrome or anaphylaxis to any prior dose of the COVID-19 vaccines.
- Patients who have had a documented COVID-19 infection in the 90 days prior to starting the study

Outcomes

We will be studying the following primary outcome:

- Rates of seroconversion for SARS-CoV-2 spike antibody after 4 weeks after a booster dose of BNT162b2/mRNA-1273 COVID Vaccine in patients that were initially seronegative after standard vaccine series

We will be studying the following secondary outcomes:

- Safety of booster dose of BNT162b2 and mRNA 1273 vaccines
- Correlation between malignancy type and prior treatment type and seroconversion
- Correlation between timing of most recent cancer-directed treatment and seroconversion
- Correlation between the total number of cancer-directed treatments received and seroconversion
- Differences between booster efficacy dependent on prior vaccine type (mRNA vs. adenoviral, BNT162b2 versus mRNA-1273)
- T cell responses at baseline and 4 weeks following vaccination
- Antigen neutralization assay results at baseline and 4 weeks following vaccination

Duration of sustained immunogenicity following vaccination in seropositive patients following our cohort for 24 months following booster vaccinations

Cohort 2

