Secondary outcomes: Safety of additional booster dose of BNT162b2 vaccine, correlation between malignancy type and prior treatment type and change in mean titer, correlation between timing of most recent cancer-directed treatment and change in mean titer, correlation between the total number of cancer-directed treatments received and change in mean titer, T cell responses at baseline and 4 weeks following vaccination, Antigen neutralization assay results at baseline and 4 weeks following vaccination, duration of sustained immunogenicity following vaccination in seropositive patients, correlations with baseline immune status correlates such as lymphocyte subsets/immune globulin levels

Safety monitoring

Patients who have met all eligibility criteria as part of cohort 3 will receive the BNT162b2 vaccine study dose at the Montefiore Vaccine Center. Each patient will be observed for a minimum of 15 minutes after their vaccination to monitor for any adverse effects in the Montefiore Vaccine Center as per the Vaccine Center protocol.

Methods

We will employ several methods for patient identification/recruitment.

- Using EPIC EMR and Montefiore Einstein Cancer-Center's Quality 360 team, we will identify patients that have undergone SARS-CoV-2 spike antibody testing. Patients with a test will then be checked if they have completed the full vaccination series for one of the FDA's Emergency Use Authorized COVID vaccines (i.e. 2 doses of the mRNA-based mRNA- 1273 (Moderna) or BNT162b2 (Pfizer/BioNTech) or a single dose of the adenovirus- based Ad26.COV2.S (Johnson & Johnson) vaccine and at least 14 days have passed since the second dose of the mRNA-based vaccines (Moderna or Pfizer/BioNTech) or 28 days have passed since the adenovirus-based Johnson & Johnson vaccine. If patients meet the above criteria, they will be offered participation in our study.

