Patients will undergo spike antibody testing at D0 of the study and then return for a study visit four weeks after their booster vaccine to complete a SARS-CoV-2 spike antibody test and T cell response assays to determine virus neutralizing activity. Side effects to the booster dose will be noted via a questionnaire that patients would fill out at this visit which will collect data pertaining to side effects and their severity compared to prior vaccine doses. Patients will return for a final study visit five to six months after their booster vaccine to assess for long-term side effects and to obtain SARS-CoV-2 spike antibody test and T cell response assays in patients who became seropositive after 4 weeks to determine if immunogenicity is sustained.

Follow up tests for cohorts 2 and 3: Patients will undergo spike antibody testing as well as baseline laboratory studies including CBC, lymphocyte subsets, quantitative immunoglobulins, T-cell response and neutralizing activity at enrollment. Patients will then receive their 4th booster vaccine (D0). Patients will return for a study visit at least 28 days after their booster vaccine to complete a SARS-CoV-2 spike antibody

test including follow-up laboratory studies as listed above. Side effects to the booster dose will be noted via a questionnaire that patients would fill out at this visit which will collect data pertaining to side effects and their severity compared to prior vaccine doses. Patients will then return for further study visits at 3 months, 6 months and 12 months and then a final study visit 24 months after their booster vaccine to assess for long-term side effects and to obtain SARS-CoV-2 spike antibody test, T cell response assays, and other laboratory studies as above in patients who became seropositive after 4 weeks to determine if immunogenicity is sustained.

Sample size

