In the prior version of the protocol (version July 23 2021), we had outlined a careful detailed data safety monitoring plan which we have changed in light of the FDA authorization for booster dosing with the BNT162b and mRNA1273 vaccines. For patients that have received one of these mRNA vaccination series who have consented to participate in the study, data for side effects will be collected via a questionnaire that is administered at the 4 week visit.

For patients that have received adenoviral vaccine, we plan for a safety run-in when only 3 subjects from the adenoviral vaccine type will be dosed and monitored for an extended period following dosing as well as monitored closely for one week. Only if no unexpected or severe side effects (such as adverse events leading to emergency room visit, anaphylaxis, hospitalization or death) are noted during this period, will further patients be allowed to be dosed. Weekly study team meetings will be held during the initial study period while vaccinations are being performed and for at least 4 weeks afterwards to review available safety data and alert IRB and DSMC according to institutional protocols if any serious AEs are identified. In addition, our study will be monitored by the Montefiore/Einstein Cancer Center DSMC.

Due to the updated CDC recommendations published on December 16, 2021 regarding use of the Ad26.COV2.S (Johnson & Johnson) vaccine given its rare but persistent serious adverse event thrombosis with thrombocytopenia syndrome (TTS), patients in Cohort 2 will continue to fill out and receive safety questionnaires at each study visit during follow-up to screen for this rare adverse event.

Informed consent

Patients will be scheduled for a consenting visit with a member of the research group listed as consenting provider on the IRB protocol. Study rationale, alternatives, potential risks/benefits, confidentiality issues will be carefully reviewed and voluntary nature of study participation emphasized. Ample time will be provided for questions and the consenting process will be documented. If patients sign the ICF, screening will be initiated, and a copy of the consent will be given to the patient.

Risk/Benefit

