Similarly, the mRNA 1273 vaccine underwent dose finding and safety phase 1 (NCT04283461) and phase 2 (NCT04405076) trials after which in the phase 3 trial of mRNA 1273 vaccine (COVE study), approximately 30,000 participants were recruited in a randomized manner that received 2 doses of 100 μ g 1 month apart. The most common solicited adverse reactions (ARs) after the two-dose series was injection site pain (86.0%). Solicited systemic adverse events occurred more often in the Moderna COVID-19 vaccine group (54.9% and 79.4%) than in the placebo (42.2% and 36.5%) group after both the first dose and the second dose respectively and were most commonly headache, fatigue and myalgia. While the majority of these ARs were mild (grade 1) or moderate (grade 2), there was a higher occurrence of severe (grade 3) reactions in the Moderna COVID-19 Vaccine group after the first (2.9%) and second (15.8%) injections. The majority of local solicited ARs occurred within the first one to two days after injection and generally persisted for a

median of one to two days. Similar to the BNT162b2 vaccine, some reports of myocarditis and pericarditis have been reported post-mRNA 1273 vaccination (see *Full EUA Prescribing Information*¹⁷). A recent randomized controlled trial of three vs two doses of mRNA 1273 vaccine in solid-organ transplant recipients, reported that any local and systemic events were slightly more common after the third dose of mRNA-1273 than after the dose of placebo, but no grade 3 or 4 events and no cases of acute rejection occurred¹⁸.

As to safety of the Ad26.COV2.S vaccine in study COV3001, the most common local solicited adverse reaction ($\geq 10\%$) reported was injection site pain (48.6%). The most common systemic adverse reactions ($\geq 10\%$) were headache (38.9%), fatigue (38.2%), myalgia (33.2%), and nausea (14.2%) (see Tables 1 to 4). Severe allergic reactions, including anaphylaxis, have been reported following administration of the Janssen COVID-19 vaccine.

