Assessment		Screening	Initial visit	Vaccine day (D0)	D28	D150-180
Informed consent	ICF	X	X			
Demographics	Demographics	X				

	Medical history	X				
	COVID vaccine history	X				
	Inclusion/Exclusion Criteria	X				
	SARS-CoV-2 Spike antibody	X				
Safety	Vital signs		X		X	X
	SpO2		X		X	X
	Physical exam		X	X	X	X
	Document Side effects				X	X
	Side Effect Questionnaire				X	
Intervention	Vaccine administration			X		
	Vaccine questionnaire				X	
Outcome	SARS-CoV-2 Spike antibody		X		X	X
	SARS-CoV-2 Neutralization assay		X		X	X
	EUROIMMUN T-cell assay		X		X	X

Study calendar cohort 2

Assessment		Screening	Initial visit	Vaccine day (D0)	D28	D90	D180	D365	D730
Informed consent	ICF	X	X						
Demographics	Demographics	X							
	Medical history	X			X	X	X	X	X
	COVID vaccine history	X			X	X	X	X	X
	Inclusion/Exclusion Criteria	X							
	SARS-CoV-2 Spike antibody	X							
Intervention	Vaccine administration			X					
	Vaccine/safety questionnaire				X	X	X	X	X
Outcome	SARS-CoV-2 Spike antibody		X		X	X	X	X	X
	SARS-CoV-2 Neutralization assay		X		X	X	X	X	X
	EUROIMMUN T-cell assay		X		X	X	X	X	X

For study visits a 7 day window will be allowable for the 4 week follow up visit, a 14 day window will be allowable for the day 90 visit and 28 day window will be allowable for the rest of the study visits.

Study calendar cohort 3

Assessment		Screening	Initial visit	Vaccine day (D0)	D28	D90	D180	D365	D730
Informed consent	ICF	X	X						
Demographics	Demographics	X							
	Medical history	X			X	X	X	X	X
	COVID vaccine history	X			X	X	X	X	X
	Inclusion/Exclusion Criteria	X							
	SARS-CoV-2 Spike antibody	X							
Intervention	Vaccine administration			X					
	Vaccine/safety questionnaire				X	X	X	X	X
Outcome	SARS-CoV-2 Spike antibody		X		X	X	X	X	X
	SARS-CoV-2 Neutralization assay		X		X	X	X	X	X
	EUROIMMUN T-cell assay		X		X	X	X	X	X

For study visits a 7 day window will be allowable for the 4 week follow up visit, a 14 day window will be allowable for the day 90 visit and 28 day window will be allowable for the rest of the study visits.

External Site

Institution	Point of Contact	Role
EUROIMMUN	[name], [contact]	Reagents and supplies, running samples.
International Cancer Covid Vaccination Consortium	Crick Legal [contact]	Data Sharing with ICCV. DUA will be reviewed and executed to account for this activity.

References:

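### Side-effect severity is described only relative to earlier doses, with no absolute scale, so rates of severe non-serious reactions may not be estimable

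*Combined protocol and SAP*

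**What the plan says.** Safety is an aim and a secondary outcome in every cohort. For cohort 1 the outcome reads "Safety of booster dose of BNT162b2 and mRNA 1273 vaccines", and for cohort 3 "Safety of additional booster dose of BNT162b2 vaccine". Cohort 2 names the safety of its two randomized products.

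The instrument is a patient questionnaire at the four-week visit, "which will collect data pertaining to side effects and their severity compared to prior vaccine doses". The Methods section gives this description for cohort 1 and repeats it for cohorts 2 and 3. The Data and Safety Monitoring Plan confirms that this is the main source for patients with a prior mRNA series: "data for side effects will be collected via a questionnaire that is administered at the 4 week visit".

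Other safety provisions are:

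- The cohort 1 calendar has a separate row, "Document Side effects", at D28 and D150-180.
- The calendars for cohorts 2 and 3 have one safety row, the vaccine/safety questionnaire, from D28 to D730.
- The Data and Safety Monitoring Plan provides for weekly team meetings "to review available safety data and alert IRB and DSMC according to institutional protocols if any serious AEs are identified".

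The Statistical analysis section plans no safety analysis.

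**The concern.** A comparison with an earlier dose has no fixed zero. A severe reaction that follows an equally severe one is recorded as no worse, and so is no reaction after no reaction. If this is all the form collects, the trial cannot state how many patients had a severe reaction to the study dose. It also cannot set its results beside the graded rates that its own Risk/Benefit section cites for another trial.

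The reference is not fixed either. Patients have had two or three earlier mRNA doses, or one Ad26.COV2.S dose in cohort 1, and the plan does not say which dose is meant. The reference product also varies: BNT162b2 or mRNA-1273 in all cohorts, and Ad26.COV2.S as well in cohort 1. In cohort 3, prior product is what defines the two groups compared on titer.

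Grades that are not recorded at the time cannot be reliably reconstructed later.

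**Working it through.** The plan gives no expected rate, sample size or power for safety, so there is no figure to reproduce. The check is a reading of every safety provision, followed by three short calculations.

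**1. Which provisions give absolute severity?**

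| Provision | Applies to | Severity scale |
|---|---|---|
| Questionnaire (Methods) | All cohorts | Relative to earlier doses |
| Separate side-effect row (calendar) | Cohort 1 | None given |
| Vaccine/safety questionnaire (calendars) | Cohorts 2 and 3 | None given |
| Screening for thrombosis with thrombocytopenia (Data and Safety Monitoring Plan) | Cohort 2 | Absolute, but one specific event |
| Weekly review, alerts to IRB and DSMC | Whole study | Serious events only |
| Run-in rule, "such as adverse events leading to emergency room visit, anaphylaxis, hospitalization or death" | Three patients with prior adenoviral vaccine | Absolute, serious end only |

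Serious events therefore have an absolute route. Severe but non-serious reactions have none that is specified.

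**2. Why the relative answer is not enough.** Let S be the severity after the study dose and R the recalled severity after the earlier dose. The question returns whether S is above, equal to or below R. The rate wanted is P(S = severe). The same mix of worse, same and better answers is compatible with many values of that rate, because R is not fixed.

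**3. How far the reference can move within one product.** The Risk/Benefit section reports that "there was a higher occurrence of severe (grade 3) reactions in the Moderna COVID-19 Vaccine group after the first (2.9%) and second (15.8%) injections". The ratio is 15.8 / 2.9 = 5.4, so the reference depends strongly on which dose the patient has in mind.

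**4. What would happen in a comparison by prior product (illustration only).** Assume normally distributed underlying severity with unit variance, and a study dose that is severe in 5% of both groups. Assume the earlier dose was severe in 15.8% of mRNA-1273 recipients. The BNT162b2 rate is not in the documents and is varied from 3% to 15.8%. Within-patient correlation ρ is 0 or 0.5. Then

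P(worse than before) = Φ{[Φ⁻¹(0.05) − Φ⁻¹(p_prior)] / √(2(1−ρ))}.

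| Prior BNT162b2 severe rate | ρ | Worse, prior BNT162b2 | Worse, prior mRNA-1273 | Gap (points) |
|---|---|---|---|---|
| 3% | 0 | 56.6% | 32.5% | 24.1 |
| 3% | 0.5 | 59.3% | 26.0% | 33.3 |
| 8% | 0 | 43.3% | 32.5% | 10.8 |
| 8% | 0.5 | 40.5% | 26.0% | 14.5 |
| 15.8% | 0 or 0.5 | 32.5% or 26.0% | 32.5% or 26.0% | 0 |

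The study dose acts identically in both groups, yet the gap runs from 0 to 33 points. It is governed by a rate that the documents do not give, and it vanishes if the earlier doses were equally severe.

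**5. What an absolute count would offer.** With no severe reactions in n patients, the one-sided 95% upper limit is 1 − 0.05^(1/n). At the planned sizes this is 1.2% for n = 250 (cohort 1), 3.0% for n = 100 (cohort 2) and 3.7% for n = 80 (cohort 3). For one cohort 2 arm after 5% dropout (100 × 0.95 / 2, about 48), it is 6.0%. A purely relative answer supports no such statement.

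**The case against.** The strongest reply is that the questionnaire itself is not in the documents. The sentence can be read as collecting side effects and, in addition, a comparison with earlier doses, so the form may already hold absolute items. That cannot be excluded, and it is why the conclusion is that the rates may not be estimable rather than that they cannot be. If the form does hold such items, one sentence in the Methods section settles the matter.

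Serious events are not lost. They have the IRB and DSMC route, and patients are observed after dosing and given a 24-hour contact. This stands, and it limits the point to severe non-serious reactions. The extra row in the cohort 1 calendar helps less, because it carries no scale and cohorts 2 and 3 have no such row.

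In cohort 2, randomization balances prior product in expectation, although the stratification factor is antibody level and not prior product. The differing reference therefore creates no systematic bias between those arms. What is lost there is the absolute severity, in the only randomized comparison of products.

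Safety is also a secondary outcome in a study that calls itself exploratory. That bears on priority, but not on whether the outcome can be reported.

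**Conclusion.** The point holds in a limited form. The only severity measure described for side effects is relative to earlier doses, with no named reference and no absolute scale for the study dose. Serious events can be counted. Rates of severe non-serious reactions may not be estimable in any cohort, and that includes a comparison between the arms of cohort 2. This assumes that the form collects no more than the Methods section describes.

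Two stronger readings are not supported.

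- A reader might infer that a planned safety comparison by prior product in cohorts 1 and 3 is biased. No such comparison is planned. Cohort 1 states its prior-product contrast for efficacy, cohort 3 states its contrast for titers, and the Statistical analysis section contains no safety test. Confounding by the reference would arise only if someone made the comparison, and its size cannot be derived from the documents.
- A reader might try to count masked severe reactions in cohort 3. With 80 × 0.95 = 76 evaluable and 30-40% primed with mRNA-1273 (22.8 to 30.4 patients), a 15.8% reference and an assumed 25-75% recurrence give 0.9 to 3.6. The 2.9% reference gives 0.2 to 0.7. The third-dose transplant trial cited under Risk/Benefit, which reported no grade 3 or 4 events, would put the count near zero. The recurrence share is assumed and carries a reaction over from one product to another. Patients whose earlier reaction led to an emergency visit or hospitalization are also excluded. No count can be defended.

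This is a worthwhile, inexpensive improvement and does not affect any primary analysis.

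**What to change.** In the Methods description of the follow-up visits, and on the existing questionnaire, record each reaction to the study dose on an absolute scale: none, mild, moderate or severe, plus whether it led to an emergency visit or hospitalization. Define the safety outcome as the proportion of patients at each grade, reported per cohort and by arm in cohort 2, and add a sentence to the Statistical analysis section saying so. Keep the comparison with earlier doses as a descriptive item only, and name the dose that it refers to.

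The cost is a few more lines on a form already in use and a sentence or two in the plan. The form becomes slightly longer for patients. No extra visit or staff is needed.

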There is emerging data that a mix and match strategy of boosting with a different COVID-19 vaccine could yield a more robust response. In addition, recent data from Johnson & Johnson demonstrate good safety and an excellent secondary immune response with 9-fold increase in neutralizing antibody levels with a booster dose of the Ad26CoV2.S vaccine. Preliminary results from cohort 1 of our study do indeed show that while a significant percentage of patients respond to a booster dose of an mRNA vaccine, however many patients either do not respond or respond with very low antibody titers suggestive of low level immunity. This poses the question whether a switch vaccine approach might be more effective at achieving

strong anti-Covid immunity. Thereby, our study in cohort 2 will address the key question of achieving a detectable immune response in poor responders to prior series of mRNA vaccinations by a randomized study design randomizing eligible patients between the Pfizer BNT162b2 vs the AdCoV2.S vaccine with reaching positive SARS-CoV-2 Spike IgG titers above a pre-established threshold by 4 weeks following vaccinations as the primary endpoint with further secondary endpoints regarding safety, neutralization antibody and T cell assays and durability of response with assessments at 3, 6, 12 and 24 months.

Our proposed study is a prospective randomized study which will aim in an exploratory/pilot fashion to assess the following variables in a population of patients with cancer with poor response to prior vaccination against COVID-19.

- 1. To study the seroconversion for SARS-CoV-2 spike IgG in patients with cancer after administering an additional booster dose of the BNT162b2 or AdCoV2.S vaccine determined in a randomized fashion
- 2. To study safety and side effects from an additional booster dose of the BNT162b2 or AdCoV2.S vaccine

Cohort 2

Our target population consists of patients with a known or previous diagnosis of cancer who had received three prior doses of one of the mRNA based COVID-19 vaccines including a booster dose

Inclusion criteria:

Above the age of 18

Have a diagnosis of prior or active malignancy- either hematological or solid tumor

Have a negative or low-level SARS-CoV-2 spike IgG after at least 14 days of booster vaccination series irrespective of active/inactive cancer status, on observation, or active therapy.

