Have received an FDA authorized booster dose of mRNA (BNT162b2 or mRNA 1273) vaccine at least 28 days before study enrollment

Exclusion Criteria

Patients who have had a serious adverse reaction to any prior COVID-19 vaccines resulting in emergency room visit or hospitalization, had events related to myocarditis, thrombosis and thrombocytopenia syndrome or anaphylaxis to any prior dose of the COVID-19 vaccines.

Patients who have had a documented COVID-19 infection in the 90 days prior to study enrollment

Outcomes

Primary outcome: Rates of seroconversion for SARS-CoV-2 spike antibody after 4 weeks following an additional booster dose of BNT162b2/AdCov2.S COVID vaccine in patients that had a poor serological response after standard vaccine series (allowing additional booster dose)

Secondary outcomes: Safety of booster dose of BNT162b2 and AdCov2.S vaccines, correlation between malignancy type and prior treatment type and seroconversion, correlation between timing of most recent cancer-directed treatment and seroconversion, correlation between the total number of cancer-directed treatments received and seroconversion, differences between booster efficacy dependent on prior vaccine type (BNT162b2 versus mRNA-1273), T cell responses at baseline and 4 weeks following vaccination, Antigen neutralization assay results at baseline and 4 weeks following vaccination, duration of sustained immunogenicity following vaccination in seropositive patients, correlations with baseline immune status correlates such as lymphocyte subsets/immune globulin levels

Safety monitoring.

Patients who have met all eligibility criteria will then be randomized 1:1 to receive either the BNT162b2 or AdCov2.S and then will be scheduled to receive their study dose at the Montefiore Vaccine Center. Each patient will be observed for a minimum of 15 minutes after their vaccination to monitor for any adverse

effects in the Montefiore Vaccine Center as per the Vaccine Center protocol.

Cohort 3

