Patients would serve as their own control. Baseline seropositivity rate by definition is 0% for the cohort but anticipating natural and laboratory variation we have based on statistical null hypothesis around a 10% seropositivity rate at 4 weeks and anticipate that booster vaccination will increase this to higher than 30%.

Planned intervention

Cohort 1

The planned intervention is to administer a booster dose of the BNT162b2 (Pfizer/BioNTech) or mRNA-1273 (Moderna) vaccine to patients that meet FDA/CDC criteria of cancer on active therapy or patients that have received a stem cell transplantation or CAR-T cell therapy in the last 2 years or those that have a negative spike IgG after having = completed one of the FDA's Emergency Use Authorized vaccination series for COVID-19 (i.e. 2 doses of the mRNA-based mRNA-1273 (Moderna), BNT162b2 (Pfizer/BioNTech), or a single dose of the adenovirus-based Ad26.COV2.S (Johnson & Johnson) vaccine, following completion of their vaccination series.

Cohort 2

The planned intervention is to administer an additional booster dose of the BNT162b2 (Pfizer/BioNTech) or Ad26.COV2.S (Johnson & Johnson) vaccine to patients that meet eligibility criteria for cohort 2 in a 1:1 randomization fashion with negative spike antibody vs. low positive antibody level serving as a stratification factor to ensure controlling for key confounder.

Cohort 3

The planned intervention is to administer an additional booster dose of the BNT162b2 (Pfizer/BioNTech) vaccine to patients that meet eligibility criteria for cohort 3 in a prospective single arm fashion in patients that had a poor serological response after standard vaccine series (including a third dose).

Participant recruitment

The study will both utilize data from the electronic health record to identify patients meeting the above inclusion criteria and enroll them on to the study and accept patients self-referred or referred by their provider at Montefiore Medical Center or external institutions. A consenting visit will be scheduled with each prospective patient. Following a carefully conducted and documented informed consent process subjects who consent for study participation will then be screened. Patients who qualify for booster COVID-19 vaccination as per FDA/CDC guidance and study criteria will then participate in our study.

Data and Safety Monitoring Plan

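### Later immunogenicity tests are limited to week-4 seropositive patients in the Methods but scheduled for everyone in the calendars; a cohort 2 durability comparison among responders would not be protected by randomisation

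*Combined protocol and SAP*

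**What the plan says.** The combined protocol and SAP describes later sampling in four places, and they do not agree.

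- **Methods, follow-up tests for cohorts 2 and 3.** Patients return at 3, 6, 12 and 24 months. Spike antibody, T-cell and other laboratory tests are obtained "in patients who became seropositive after 4 weeks to determine if immunogenicity is sustained". The paragraph before it uses the same words for the cohort 1 visit at five to six months. Neither gives the titer that counts as seropositive.
- **Outcomes, cohorts 2 and 3.** The secondary outcome is "duration of sustained immunogenicity following vaccination in seropositive patients".
- **Cohort 2, introduction.** Durability is a secondary endpoint of the randomised cohort, without that limit: "durability of response with assessments at 3, 6, 12 and 24 months".
- **Study calendars.** For cohorts 2 and 3, the spike antibody, neutralization and T-cell assays are marked at D90, D180, D365 and D730. The only note is on visit windows (for example, "a 14 day window will be allowable for the day 90 visit"). The cohort 1 calendar marks the same assays at D150-180, also without a restriction.

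Cohort 2 patients are "randomized 1:1 to receive either the BNT162b2 or AdCov2.S", with "negative spike antibody vs. low positive antibody level serving as a stratification factor" (Planned intervention). The Sample size section plans for 25% seroconversion with BNT162b2 and 50% with Ad26.COV2.S, against a threshold of 1000 AU/mL. The Statistical analysis section gives no method for durability and no rule for patients who had not responded by week 4.

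**The concern.** There are two problems.

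The first is operational. A site that follows the Methods text and a site that follows the calendar will draw samples from different patients, and samples not taken cannot be recovered.

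The second is inferential. In cohort 2, serostatus at week 4 is the primary outcome, and the plan expects the vaccine to change it. Selecting on it leaves a different mix of patients in each arm. If one vaccine also converts weaker responders, its responder group contains patients who may lose antibody sooner. It can then look less durable among responders even when at least as many of its randomised patients remain above threshold. Stratifying by baseline antibody does not repair selection on something measured after randomisation.

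The restriction also gives up information. Late conversion would not be seen, nor would later titers, T-cell responses or neutralization in patients without an antibody response. The Methods add those assays precisely because spike IgG may not track neutralizing activity.

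**Working it through.** **1. The plan's own figure.** Inputs from the Sample size section: 25% versus 50%, alpha 0.05, power 80%, 1:1. With pooled variance, no continuity correction and a one-sided test:

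n = [1.645·√(2·0.375·0.625) + 0.842·√(0.25·0.75 + 0.5·0.5)]² / 0.25² = (1.126 + 0.557)² / 0.0625 = 45.3, so 46 per group.

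This matches the stated 46. (A two-sided test would need 58; sidedness is not stated for cohort 2, which is a separate matter.) No sample size or precision is given for durability.

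**2. Size of the responder set.** With 100 patients and the plan's 5% dropout, 100 × 0.95 / 2 = 47.5 per arm.

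- BNT162b2: 47.5 × 0.25 = 11.9, about 12.
- Ad26.COV2.S: 47.5 × 0.50 = 23.75, about 24.
- Non-responders: (0.75 + 0.50) / 2 = 62.5% of patients would have no antibody or T-cell data after week 4.

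**3. What selection can do (assumed inputs).** Suppose 25% of patients would respond to either vaccine, 25% only to Ad26.COV2.S, and 50% to neither, with no late conversion. This fits the planned rates if every BNT162b2 responder would also respond to Ad26.COV2.S. Let 80% of the first group stay above threshold in either arm, and let a fraction d of the second group do so. Then:

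- Responders only: BNT162b2 0.80; Ad26.COV2.S (0.25·0.80 + 0.25·d) / 0.50.
- All randomised: BNT162b2 0.25·0.80 = 0.20; Ad26.COV2.S 0.20 + 0.25·d.

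| d (assumed) | Responders: BNT162b2 vs Ad26.COV2.S | Difference | All randomised: BNT162b2 vs Ad26.COV2.S | Difference |
|---|---|---|---|---|
| 80% | 80% vs 80% | 0 | 20% vs 40% | +20 |
| 60% | 80% vs 70% | -10 | 20% vs 35% | +15 |
| 40% | 80% vs 60% | -20 | 20% vs 30% | +10 |
| 20% | 80% vs 50% | -30 | 20% vs 25% | +5 |
| 0% | 80% vs 40% | -40 | 20% vs 20% | 0 |

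Differences are Ad26.COV2.S minus BNT162b2, in percentage points.

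**4. A second assumed model.** Reversal is not inevitable. Let log10 titers at week 4 be normal with SD 0.8, centred to give 25% and 50% above 1000 AU/mL (means 3 − 0.8 × 0.674 = 2.46 and 3.00). Let both arms then fall by 0.6 log10 on average, with added variation of SD 0.3. By simulation, 9% versus 24% of all randomised are still above threshold, and 36% versus 48% of responders. The direction is kept, but the geometric mean titer ratio shrinks from 3.5 in all randomised to 1.5 in responders. With SD 0.5 the ratios are 2.2 and 1.3; with SD 1.1 they are 5.5 and 1.7.

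**5. Precision of the responder contrast.** At 80% versus 60% in 12 versus 24 patients, the 95% half-width is 1.96·√(0.16/12 + 0.24/24) = 0.30, or 30 percentage points.

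**The case against.** A reader might infer that the restriction breaks the cohort 2 randomised comparison, or that the cohort can then give no unbiased answer on durability. The documents do not support either reading. The primary comparison is at week 4 and covers all patients, and the safety questionnaires continue at each visit. The plan specifies no between-arm test of durability and calls the cohort exploratory. Duration among responders is a legitimate description of responders.

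Restricted sampling also does not by itself rule out a randomised comparison. The all-randomised results in the table use only data from week-4 responders, because non-responders contribute zero. Having responded at week 4 and still being above threshold can be determined for every randomised patient who stays in follow-up, whichever sampling rule is used. This objection stands. It narrows what restricted sampling strictly loses to late conversion, and titers and T-cell and neutralization durability in non-responders.

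The Methods clause might also be read as stating a purpose, or as limiting only the last item in its list. The calendars, the cohort 2 introduction and the Methods statement that six tubes are collected from each patient at each draw all favour sampling everyone. That shows that the passages conflict; it does not resolve them. The outcome definitions point towards the restriction, and the plan never says that non-responders count as not sustained.

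Finally, the size of the distortion is assumed. With equal persistence in both groups of responders, the responder-only difference is 0.

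**Conclusion.** The contradiction is real and should be removed. The Methods limit the later tests to week-4 seropositive patients in all three cohorts, and the calendars do not. In cohort 2, any between-arm durability comparison among responders would lack the protection of randomisation, rest on about 12 versus 24 patients, and could hide or reverse a difference.

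The counts rest on the plan's 25% and 50% rates and on its 5% dropout allowance holding through later visits. The ranges of 0 to -40 points and +20 to 0 points rest on assumed persistence rates and on the assumed responder groups. They show what could happen and are not predictions. The point concerns a secondary endpoint.

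**What to change.** 1. In the Methods, delete the restriction to patients seropositive at 4 weeks for all three cohorts, so that the scheduled spike, neutralization and T-cell assays are done in every patient as the calendars show. State separately who has the blood count, lymphocyte subsets and immunoglobulins at later visits, since the calendars do not list these.
2. For cohort 2, define the between-arm durability measure as the proportion of all randomised patients with spike IgG above 1000 AU/mL at 3, 6, 12 and 24 months, stratified by baseline serostatus (negative versus low positive). If non-responders are not sampled, say that they count as not sustained.
3. Keep duration among responders as a descriptive summary within each arm, and state the titer that defines seropositive.

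The change is a text edit to Methods, Outcomes and Statistical analysis. Its downside is running assays in non-responders if the site had planned to skip them. In cohort 2, with 50 per arm and no dropout, that is at most about 62.5 patients × 4 visits = 250 assay sets, all of which the calendar already schedules for spike, neutralization and T-cell testing.
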